12.2.2 Secondary Endpoints

12.2.2.1. *Objective Response Rate (ORR)*

Objective response rate (ORR) is defined as the number of subjects with a best response of CR or PR after 12 weeks of therapy by RECIST 1.1 criteria divided by the number of randomized subjects as described in Section 10.3.4.2

12.2.2.2. *Time to progression (TTP)*

TTP is defined as the time from the start of study drug to the first documented tumor progression or recurrence of tumor as determined by the investigator using RECIST 1.1 or iRC criteria. Patients who are alive and free of known progression at the time of analysis will be censored on the date of last tumor assessment.

12.2.2.3 *PFS*

PFS is defined as the time from the start of treatment to date of PD or recurrence or date of death whichever occurs first if patients have a event, or to the last follow-up date if patients are alive without PD.

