After finishing the last treatment, hepatic resection or biopsy will occur on day 1 of week 7 (+/- 7 days). We will obtain surveillance scans (MRI of abdomen and pelvis with/without contrast, and CT chest with/without contrast of chest) 8 weeks after surgery. Patients who show significant progression of disease post-operatively will be taken off study and an optional biopsy will be taken at that time for immunological analysis.

Patients who complete the study or discontinue study treatment should be scheduled for an end of treatment visit (EOT) as soon as possible. All patients who complete the study or discontinue treatment will have a safety follow-up visit 30 (+/- 14 days) after the last dose of study drug or surgery, whichever comes last. Please refer to **Figure 2** below for the study design.

Patients will receive baseline staging studies with CT or MRI and be assessed for treatment response by scans: MRI or CT of abdomen and pelvis with/without contrast, and CT chest with/without contrast of chest (according to RECIST 1.1 and irRC) at week 6 (+/- 7 days). Each patient will have post-surgical (day 1 of week 11 +/- 7 days), staging studies as above. Subsequently, restaging will be carried out every 12 weeks unless, in the investigators' opinion, follow-up intervals need to be shorter. Studies to confirm a complete response or document progressive disease will be performed as needed. Patients will be allowed to continue study therapy after initial investigator-assessed RECIST 1.1/irRC-defined progression if they are deemed by the investigator to be deriving clinical benefit and tolerating study drug(s), as described in Section 8.3.

[figure not shown]

Figure 2. Study Design of preoperative nivolumab alone or in combination with ipilimumab. There are 2 arms to this study: A) Nivolumab monotherapy in resectable HCC; B) Combination nivolumab plus ipilimumab in resectable HCC.

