- h. Blood will be collected prior to dose one (C1D1), Cycle 2 and 3 (before the 2nd and 3rd dose of Nivolumab), at time of surgery (C4D1), at 8 weeks after surgery (C6D1), at every restaging thereafter (q12 weeks), and finally at treatment discontinuation (confirmed progression or end of therapy).
- i. Screening tumor imaging will be performed within 28 days prior to allocation for confirmation of baseline measurable disease per RECIST 1.1 as required prior to subject allocation, then at time of surgery. After surgery, imaging will be repeated and therapy starts at C7D1, then surveillance imaging will be repeated q12W (72 \pm 7 days).
- j. Biopsies will be required pre-treatment and at time of surgery.
- k. The first on-study imaging time point will be performed at 6 weeks around time of surgery (42 \pm 7 days) calculated from the date of allocation and then 8 weeks after surgery, and will continue to be performed q12W.
- l. SAEs will be followed through 100 days following cessation of treatment, or 100 days following cessation of treatment if the subject initiates new anticancer therapy, whichever is earlier.
- m. HBV/HCV viral loads (for subjects who have known history of chronic infection) will be measured during screening, then at C1D1, at time of surgery (C4D1), at 8 weeks after surgery (C6D1), at every restaging thereafter (q12 weeks), and at time of discontinuation.
- n. The following imaging studies are required at screening, at time of surgery, at 8 weeks after surgery, then at every restaging thereafter (q12 weeks): CT chest with or without contrast; MRI of abdomen and pelvis with or without contrast unless patient has contraindication for MRI or severely claustrophobic.
- o. Every time imaging is done for re-staging (q12 weeks).

Trial Period:	Screening Phase	Treatment Cycles. 3 cycles (2-Week Cycles) planned before surgery then after surgery (4-Week Cycles), patients may receive up to 2 years of therapy depending on response and every restaging scans every 12 weeks							End of Treatment	Post-treatment		
Title:	Screening				Surgery				Discontinue	Safety Follow-up ^l	Follow-Up Visits	Survival Follow-Up ^a
Treatment Cycle/Day:	0	C1D1	C2D1	C3D1	C4D1	C5D1	C6D1	C7+D1	At time of discon	30 days post last dose	Every 9 weeks post-discon	Every 12 weeks
Scheduling Window (Days) ^b	-28 to -1	±3	±3	±3	±7	±3	±3	±3	±3	±7	±7	±7

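### ORR is read at 12 weeks (week 14 in the summary reports), after the planned week-7 resection, and no rule keeps post-operative scans out of it

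*Combined protocol and SAP*

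**What the plan says.** **ORR.** The numerator in Section 12.2.2.1 is "the number of subjects with a best response of CR or PR after 12 weeks of therapy by RECIST 1.1 criteria"; the denominator is all randomized subjects. The Safety/Efficacy Summary Reports at the end of Section 12.6 read toxicity at week 6 and response at week 14.

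**Surgery.** Section 5.3 states that "hepatic resection or biopsy will occur on day 1 of week 7 (+/- 7 days". It expects 1–3 of 30 patients to miss resection because of rapid progression. Section 12.1 gives a looser limit: within 4 weeks of the end of the last cycle.

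**Imaging.** Section 5.3 says "Patients will receive baseline staging studies with CT or MRI and be assessed for treatment response by scans", "according to RECIST 1.1 and irRC) at week 6 (+/- 7 days". The later scans are described there as surveillance, staging or restaging. The first post-operative scan has more than one date:

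- One sentence of Section 5.3: "Each patient will have post-surgical (day 1 of week 11 +/- 7 days), staging studies as above".
- Another sentence of Section 5.3: "CT chest with/without contrast of chest) 8 weeks after surgery". Table 1 footnote n agrees, with imaging "required at screening, at time of surgery, at 8 weeks after surgery"; so do footnote k and Sections 10.1.2 to 10.1.5.
- Footnote i links post-operative imaging to C7D1.

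**Scoring.** Section 10.3.4.2 lets best response run up to progression or recurrence. Its complete-response rule asks only that no target lesion remain and makes no exception for lesions taken out at surgery. Section 10.1.5 continues to follow clinical response after the operation. Section 10.3.4.4 dates response from the first of a confirming pair of measurements.

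**Use.** In Section 12.6 one response in an arm is the signal for larger studies, and none means that the treatment is ineffective.

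**The concern.** ORR is meant to show whether drug given before surgery shrinks tumor. A scan taken after the tumor has been removed cannot show that. The ORR definition neither cites the week-6 scan nor stops at resection, so an analyst following it could let a clear post-operative scan enter as a complete response.

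ORR is a secondary endpoint, but it carries a go/no-go rule that turns on a single patient. The same binary response also enters the Fisher comparison of the arms and the tests relating response to immune markers.

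**Working it through.** **1. The plan's own figure.** Section 12.6 says that with 15 treated patients and a true rate of 15%, the chance of at least one response exceeds 90%. Check: 1 − 0.85^15 = 0.913. The figure is correct and does not depend on when response is read.

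**2. One calendar.** Day 1 is the first dose.

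| Event | Arithmetic | Study day |
|---|---|---|
| Week-6 scan (5.3; footnote k) | 42 ± 7 | 35–49 |
| Planned resection (5.3) | 6 × 7 + 1 = 43, ± 7 | 36–50 |
| Latest resection under 12.1 | cycle 3 ends day 42; 42 + 28 | 70 |
| Week-11 post-surgical staging (5.3) | 10 × 7 + 1 = 71, ± 7 | 64–78 |
| End of 12 elapsed weeks | 12 × 7 | 84 |
| Week 14 (12.6) | 13 × 7 + 1 to 14 × 7 | 92–98 |
| Scan 8 weeks after surgery | 43 + 56 = 99; 36 + 56 to 50 + 56 | 92–106 |

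Day 84 and week 14 both fall after the planned resection, and after the latest date that Section 12.1 allows. If the 12 weeks are counted as weeks on drug (6 before surgery, then 6 of adjuvant therapy from day 43 + 28 = 71), they end later still, on day 112.

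**3. Which scans each reading admits.**

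- *Through week 12, staging at week 11:* the post-operative scan (days 64–78) falls before day 84, so it is admitted.
- *Through week 12, scan 8 weeks after surgery:* the post-operative scan (days 92–106) falls after day 84. Only the pre-surgical scan counts.
- *After week 12, either schedule:* post-operative imaging is admitted.
- *Week 14, scan 8 weeks after surgery:* the nominal scan is day 99 and week 14 ends on day 98. An operation or scan early in its window could bring it into week 14; the nominal date does not.

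**4. How many patients this touches.** 30 − 3 = 27 to 30 − 1 = 29 of the planned 30 are expected to be resected (90–97%).

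**5. Effect of one misattributed response.** With 27 randomized, the smaller arm has at most 13 patients. Exact (Clopper–Pearson) 90% intervals:

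- 0/13: 0–20.6%, read as ineffective.
- 1/13 = 7.7%: 0.4–31.6%, read as a signal.

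**6. Frequency.** The documents give no rate. Purely as an assumption, let q be the per-patient chance that a post-operative scan is scored as response because of surgery, with no drug activity and 15 patients. Then P(at least one) = 1 − (1 − q)^15: 0 at q = 0, 0.537 at 5%, 0.794 at 10% and 0.987 at 25%. This shows how sensitive the rule is; it does not estimate what happened.

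**The case against.** The strongest reply is that the plan already points to the right scan. Section 5.3 ties treatment response to week 6 and describes later imaging in other terms. The 12-week wording can be read as best response through week 12; with the first post-operative scan 8 weeks after surgery, the timing stated most often, only the pre-surgical scan then qualifies. This stands as one tenable reading, but Section 12.2.2.1 does not adopt it, the week-11 sentence defeats it, and the week-14 reading in Section 12.6 looks past it.

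A reader might infer more than the documents support, in three ways:

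- *That the plan scores resection as complete response.* No passage says so. ORR is to follow RECIST 1.1, and how that guideline treats resected lesions cannot be checked from these documents. What is shown is that the written rules do not prevent it.
- *That week 14 necessarily takes in the post-operative scan.* It could, but the nominal date is one day later.
- *That every patient is resected before week 12.* Section 7.0 lets surgery wait for an adverse event to settle, and Section 12.2.1 counts a delay as an extreme toxicity only beyond 3 months. Some patients may be unresected at 12 weeks.

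Two further objections are sound. Patients without an evaluable scan already count as non-responders through the randomized denominator, so the lack of a not-evaluable row in Table 4 does not change ORR. And ORR is not the only guide: Section 12.6 also uses TTP, the 6-month clinical benefit rate and confidence intervals.

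**Conclusion.** The point holds as a flaw in the stated rule and should be fixed before the final response analysis. ORR is read after the planned resection of 90–97% of patients, and nothing in Sections 12.2.2.1, 12.6 or 10.3.4.2 confines it to pre-resection imaging. One post-operative response in an arm with no drug response would turn the stated conclusion from ineffective to signal, and would carry into the Fisher test and the biomarker associations.

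The conclusion rests on the written definitions and the planned calendar. It does not establish that any response was miscounted or that ORR is inflated. The primary safety endpoint is not affected.

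A separate minor note: the statement of more than 90% is true for 15 per arm. With 27 randomized, at least one arm has 13 or fewer, giving at most 1 − 0.85^13 = 0.879; an arm of 14 would give 1 − 0.85^14 = 0.897.

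**What to change.** 1. In Section 12.2.2.1, define ORR as RECIST 1.1 CR or PR versus baseline on scans done before resection, divided by randomized patients. Use the scheduled week-6 scan, or the last pre-resection scan if surgery is delayed; for patients never resected, use scans through week 12. Anchor this on the date of resection, because the scan and surgery windows overlap (days 36–49).
2. State that post-resection scans do not count toward ORR and serve only to detect recurrence for TTP and PFS.
3. State that ORR is unconfirmed, and reconcile this with the paired measurements in Section 10.3.4.4.
4. Align the week-14 response reading in Section 12.6, and use the one definition for the one-response signal, the Fisher test and the biomarker associations.
5. Reconcile the post-operative scan timing (week 11, 8 weeks after surgery, and C7D1 in footnote i). In footnote k, Arm B puts 8 weeks beside 42 ± 7 days, while Arm A has "The first on-study imaging time point will be performed at 6 weeks around time of surgery".
6. Record all this as a dated, justified clarification before the final response analysis. List separately any response already called on a post-operative scan, and re-check earlier summary reports.
7. Report the probability of at least one response for the actual arm sizes.

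**Cost.** No new procedure is needed, since the pre-surgical scan is already scheduled in both arms. The price is a change of definition after data have accumulated in an open-label trial. Response would also rest on a single unconfirmed scan in most patients, and ORR may come out lower.

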12.2.3 Exploratory Endpoints

Tissue and blood immune monitoring will be conducted through the Immunotherapy Platform based on samples collected at the following time points: 1) Pre-treatment; 2) time of surgical resection or biopsy (if unresectable); and 3) at time of discontinuation (peripheral blood collection).

12.3 Sample Size

Up to 30 patients will be enrolled, for 15 patients each in arm. This sample size is based on having sufficient patients to assess toxicities in each arm while providing preliminary estimates of secondary endpoints for future trials.

12.4 Randomization

Patients in the resectable cohorts will be randomized in a 1:1 fashion through the Clinical Trial Conduct website (<https://biostatistics.mdanderson.org/ClinicalTrialConduct>), which is housed on a secure server at MDACC and maintained by the MDACC Department of Biostatistics. Access to the website will be gained through usernames and passwords provided by the MDACC Department of Biostatistics to personnel responsible for enrolling patients. Training on the use of

the Clinical Trial Conduct website to enroll patients on the study will be provided by the study biostatistician for study personnel.

12.5 Safety Monitoring

All patients who receive at least one dose of nivolumab or nivolumab plus ipilimumab will be considered evaluable for toxicity.

Safety assessments will include a comprehensive evaluation of AEs and/or toxicity based on:

- Results of monitoring vital signs (blood pressure, heart rate, respiratory rate, and body temperature)
- Results of clinical chemistry, hematology/coagulation, complement testing, thyroid function testing, and urine analysis tests
- ECG results
- Changes in physical examination
- Need for concomitant medications
- ISRs
- ECOG performance status

12.6 Data Analyses

This is a two arm, open-label pilot study evaluating nivolumab alone or in combination with ipilimumab in the preoperative or prebiopsy setting. Since no effective treatments are available in this setting, a response rate of 15% (within 95% CI) is considered acceptable – i.e., the signal for launching further, larger studies with nivolumab or nivolumab + ipilimumab in this patient population is ≥ 1 response in the current study (each arm). If no response is observed, the treatment with nivolumab alone or in combination with ipilimumab will be considered ineffective. A total of 15 patients will be enrolled in each arm and treated to rule out a response rate of 15% or less with 90% power when at least one response is observed. In other words, with 15 patients treated, the probability of observing at least one response is more than 90% if the response rate is at least 15%. Descriptive statistics including with 90% confidence interval will be computed. Observed response profile, clinical benefit rate at 6 months and TTP along with relevant confidence intervals will be used to guide future development decisions.

Total evaluable patients	Number of responders	Response rate	Lower 90% CI*	Upper 90% CI*
15	0	0%	<1%	18%
15	1	7%	<1%	27%
15	2	13%	2%	36%
15	3	20%	6%	44%
15	4	27%	10%	51%
15	5	33%	14%	58%
15	6	40%	19%	64%
15	7	47%	24%	70%
15	8	53%	30%	76%
15	9	60%	36%	81%
15	10	67%	43%	86%
15	>10**	>67%	>43%	>86%

* Exact confidence interval computed by the method of Clopper and Pearson (Biometrika 26:404-413, 1934)

The Kaplan-Meier method will be used to estimate probability of PFS for each treatment arm.

Our exploratory objectives are to characterize the immune response for both treatment arms and its correlation to treatment response. Immune responses, such as infiltration of CD8+/CD4+ T cells and dendritic cells, and cytokine levels in blood, will be compared between pre-treatment and post-treatment via paired t-test and Wilcoxon signed rank test. The overall treatment response rate will be summarized descriptively by dose with the n, percentage, and 95% CIs. Comparison of the response rates between two treatment arms will be made via Fisher's exact test Association

between the binary overall treatment response and immune responses will be assessed by two-sample t-test and Wilcoxon rank sum test.

The Investigator is responsible for completing a Safety/Efficacy Summary Report, and submitting it to the IND Office Medical Affairs and Safety Group, for review and approval. This should be submitted after the first 5 evaluable patients per arm, complete 14 weeks of study treatment, and every 5 evaluable patients per arm, thereafter. On every summary submission, toxicity will be assessed at week 6, and response at week 14 of study treatment.

A copy of the cohort summary should be placed in the Investigator's Regulatory Binder under "sponsor correspondence".

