3.3.2 Nivolumab in Hepatocellular Carcinoma

El-Khoueiry AB, et al. presented results from the interim analysis of the phase 1/2 nivolumab trial (CA209-040) in patients with advanced hepatocellular carcinoma at the 2015 annual ASCO meeting [34]. In the presentation, the dose escalation study demonstrated safety and tolerability of nivolumab at 0.1 mg/kg to 10 mg/kg in patients with HCC due to HCV, HBV or who were uninfected with viral hepatitis. The only grade 4 adverse event was elevated lipase (1 patient) while grade 3 elevations in liver enzymes were seen in 9 patients (AST = 5, ALT = 9). 3 mg/kg was selected for the dose expansion in the uninfected and HCV cohorts; the dose escalation for the HBV cohort was ongoing. In 42 patients evaluable to response, the ORR by RECIST 1.1 criteria was 19% (8) with 2 patients achieving a complete response. The preliminary overall survival at 12 months was 62% (95% CI 42-76%). Moreover, Sangro B, et al. recently presented interim results of 214 patients in the expansion CheckMate-040 study who received Nivolumab 3 mg/kg every 2 weeks [35]. This report demonstrated a preliminary ORR = 16%.

Because of these results, a phase III study comparing nivolumab to sorafenib for patients with advanced HCC has been launched in the frontline setting with an estimated enrollment of 726 patients and primary completion date of July 2017 (NCT02576509).

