3.4.5 Study Rationale

As mentioned, surgical resection or liver transplantation are the only potentially curative treatment modalities for localized HCC in select patients. Local-regional therapies (ie: ablation, arterial-based therapies, or EBRT) can palliate and sometimes downstage non-resectable lesions, but are not typically curative procedures. Sorafenib is the only FDA-approved systemic therapy for advanced HCC. Therefore, patients with unresectable HCC have poor survival and there is a high recurrence rate (~50% or more) for those receiving potentially curative therapy. Novel treatment approaches taking advantage of the higher response rates seen in early-phase HCC studies and long-term survival of immunotherapies clearly need to be studied in order to improve the treatment of HCC. As a basis for future research in HCC, immunological pathways in response to monotherapy versus combinational therapy need to be evaluated in the context of clinical outcome in order to identify predictive and prognostic biomarkers as well as other potential therapeutic targets.

Anti-PD-1 antibody, nivolumab, has recently been shown in a phase 1-2 clinical trial on 42 patients with advanced or unresectable HCC to result in 19% ORR; many of these responses were durable with a response duration of 1-8+ months in patients achieving a PR [34]. Subsequent analysis of 214 patients on this study confirmed a 16% ORR. Of note, these response rates compare favorably to those seen for sorafenib where the ORR = 2% (without any observable CRs). Anti-CTLA-4 antibody, ipilimumab, has not been tested in HCC. However, an alternative anti-CTLA-4 blocking agent, tremelimumab, has been reported to have a partial response rate of 17% in patients with HCC and chronic HCV [42].

Based on strong preclinical data supporting the hypothesis that PD-1 and CTLA-4 are both non-redundant pathways that negatively regulate effector T cells, multiple recent clinical studies in other cancer types suggest that combination nivolumab and ipilimumab may induce even greater anti-tumor responses than either agent alone. While this combination has yet to be tested in HCC, considering the immunosuppressive environment especially characteristic of hepatitis-related HCC, combination therapy may lead to enhanced responses.

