12.0 STATISTICAL METHODOLOGY

12.1 Preliminaries and Objectives

This is a randomized, pilot trial of nivolumab (Arm A) or nivolumab + ipilimumab (Arm B) as pre-operative treatment for patients with hepatocellular carcinoma who are eligible for surgical resection. Each patient in both Arms A and B will be given nivolumab at 240 mg every 2 weeks

for a total of 6 weeks. Patients in Arm B will additionally be treated concurrently with ipilimumab at 1mg/kg every 6 weeks. No dose increases or reductions will be allowed for nivolumab or ipilimumab. Surgical resection or post-treatment biopsy will occur within 4 weeks after finishing the last cycle of therapy. The rationale is that nivolumab and ipilimumab activate the immune system via distinct mechanisms and therefore, the combination of nivolumab and ipilimumab may result in synergistic activation of the immune system against hepatocellular carcinoma. The primary objective is to assess the safety and tolerability of nivolumab +/- ipilimumab. Secondary objectives include estimating the ORR and TTP of the 2 different arms. Exploratory objectives include evaluating the pre- and post-treatment immunological changes in tumor tissues and peripheral blood.

As of January 8, 2020, 30 patients have been enrolled and 27 patients have been randomized. The PI decided to stop enrollment since the study has reached its primary endpoint of safety.

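### Section 12.6 says one or more responses in 15 rules out a response rate of 15% or less with 90% power; the 91% is the chance of a response when the rate is 15%

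*Combined protocol and SAP*

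**What the plan says.** Section 12.6 sets the efficacy signal separately for each arm. At least one response supports larger studies, and no response means the treatment is judged ineffective. The benchmark is introduced with the statement that "a response rate of 15% (within 95% CI) is considered acceptable". The 15 patients per arm are then said to be "treated to rule out a response rate of 15% or less with 90% power when at least one response is observed". The sentence after that is offered as a paraphrase: "with 15 patients treated, the probability of observing at least one response is more than 90% if the response rate is at least 15" per cent. A table of exact (Clopper-Pearson) 90% limits for 15 evaluable patients follows; its row for one responder runs from below 1% to 27%.

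Section 12.2.2.1 defines the ORR as responders "by RECIST 1.1 criteria divided by the number of randomized subjects as described in Section 10.3.4.2". Section 12.1 records that "30 patients have been enrolled and 27 patients have been randomized" when enrollment stopped. Section 12.4 says "Patients in the resectable cohorts will be randomized in a 1:1 fashion". The number in each arm is not reported.

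**The concern.** The clause and its paraphrase are different statements. The clause says that seeing a response excludes rates up to 15%. The paraphrase says that a response is likely if the rate is 15% or more. The second is a sensitivity statement about a target rate. The first treats the same 15% as a null value to be rejected. The section also calls 15% acceptable, and a rate that is acceptable cannot also be the rate that success excludes.

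The risk lies in reporting. Someone relying on the clause could write that one responder in an arm shows an ORR above 15% and use that to justify a larger study, when the data would be compatible with rates close to zero.

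**Working it through.** **Inputs.** n = 15 per arm, signal of at least 1 response, reference rate 15%, exact two-sided 90% intervals (all Section 12.6); 27 randomized (Section 12.1); ORR denominator is randomized subjects (Section 12.2.2.1).

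**1. Reproduce the plan's figure.** P(at least 1 response) = 1 − (1 − p)^n. With p = 0.15 and n = 15, this is 1 − 0.85^15 = 0.913. The paraphrase (more than 90%) is correct, and 15 is the smallest n that achieves it, since n = 14 gives 0.897.

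**2. Read the clause as a test of ORR ≤ 15%.** The probability of passing the rule at the null boundary is the same 0.913. That would be the false-positive rate at 15%, not power. At lower true rates with n = 15, the rule is still passed often:

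| True ORR | P(at least 1 of 15) |
|---|---|
| 15% | 91.3% |
| 10% | 79.4% |
| 5% | 53.7% |

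**3. What one response excludes.** The exact 90% lower limit for 1/15 solves 1 − (1 − p)^15 = 0.05, giving p = 0.3%. The upper limit solves (1 − p)^15 + 15p(1 − p)^14 = 0.05, giving p = 27.9%. The interval contains 15%.

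**4. When 15% is excluded from below.** The 90% lower limit is 14.2% at 5/15 and 19.1% at 6/15. Equivalently, at p = 0.15, P(X ≥ 5) = 0.062 and P(X ≥ 6) = 0.017, against 0.05 in each tail. Six responses are needed, not one. The plan's table shows the same, with 14% at five responders and 19% at six.

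**5. Effect of 27 randomized.** If the two arms sum to 27, the smaller has at most 13.

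| Arm size | P(at least 1), ORR 15% | 90% CI for one response | Responses for lower limit > 15% |
|---|---|---|---|
| 15 | 91.3% | 0.3% to 27.9% | 6 (19.1%) |
| 14 | 89.7% | 0.4% to 29.7% | 5 (15.3%) |
| 13 | 87.9% | 0.4% to 31.6% | 5 (16.6%) |
| 12 | 85.8% | – | – |

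The loss is small. Section 3.4.5 cites advanced disease: "Subsequent analysis of 214 patients on this study confirmed a 16% ORR". Section 3.3.2 reports that "the ORR by RECIST 1.1 criteria was 19% (8) with 2 patients achieving a complete response". At those rates n = 13 gives 1 − 0.84^13 = 89.6% and 1 − 0.81^13 = 93.5%.

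**6. The zero-response side.** The one-sided 90% upper limit for 0/n is 1 − 0.1^(1/n): 14.2% for n = 15, 15.2% for n = 14 and 16.2% for n = 13. The result that argues against 15% is therefore no response, and only just so at n = 15.

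**7. Table cells.** Recomputed exact limits differ from the printed ones in two places: 1/15 upper is 27.9% (printed 27%) and 10/15 lower is 42.3% (printed 43%). The greater-than-43% entry in the last row remains true, because the 11/15 lower limit is 48.9%.

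**The case against.** The best defence is that the section corrects itself. The next sentence gives the intended property, the operative rule is stated plainly, and the table shows how wide the interval is for one responder. Someone who reads the whole paragraph is not misled. The 90% figure itself reproduces, so the fault is one of interpretation and not of calculation. ORR is secondary, Section 12.3 rests the sample size on toxicity assessment and preliminary estimates, other outcomes also guide development, and enrollment has closed. All of that stands, and it limits the impact. It does not make the clause true: no one- or two-sided convention does, and the clause describes the plan's explicit signal for further studies.

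The arm-size point is fairly called an update and not an error. The probability sentence is conditional on 15 treated patients and remains correct on that condition. The actual split is unknown, so the values for 12 to 14 are scenarios.

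The confidence-level inconsistency is tidying. The sentence promising 90% intervals does not name response rate (the table makes the link), one mention of 95% concerns acceptability, and the other sits in the exploratory paragraph. The two table cells do not affect the decision rule.

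**Conclusion.** The clause is wrong as written. The 91.3% is the chance of passing the signal when the ORR is 15%. A single response in 15 is compatible with 0.3% to 27.9%, and excluding 15% or less at the plan's own 90% level takes 6 of 15. This rests only on a binomial model and the plan's stated n, rule and interval method.

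With 27 randomized and randomized subjects as the denominator, at least one arm has a probability of at most 87.9% under any split, a shortfall of at most 2.1 points below 90% if that arm has 13 patients. The practical effect is on interpretation and reporting; the rule, the sample size and the primary safety conclusion are untouched.

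**What to change.** In Section 12.6, end the sentence on 15 patients per arm before the claim of ruling out 15%. Keep the sentence that follows and restate it along these lines:

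> If the true ORR is 15%, the probability of at least one response is 91.3% with 15 patients, 89.7% with 14, 87.9% with 13 and 85.8% with 12. One response does not exclude an ORR of 15% or less (exact two-sided 90% CI for 1/15: 0.3% to 27.9%).

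Once the split is known, keep only the values for the actual arm sizes. A sentence on zero responses, using the limits in step 6, would be a useful optional addition.

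Also use one confidence level for response rate (90% is already in the table) and one denominator (randomized, as in Section 12.2.2.1, where the table now says evaluable). Change the 1/15 upper limit to 28% and the 10/15 lower limit to 42%.

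The cost is wording and two table cells, with no new patients or data and no change to the rule. The stated assurance becomes slightly less favourable, and 90% throughout gives narrower intervals than 95% (for 1/15, 0.3% to 27.9% against 0.2% to 32.0%).
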